## Highlights

Sarcopenia is known as a decline in muscle function and muscle mass. It is often seen in increasing age in otherwise healthy individuals and also in those with multimorbidity. Moreover, recent studies highlight that sarcopenia can establish rapidly; this is named acute sarcopenia. In this condition acute illnesses, stressors or hospitalisation lead to a decrease in muscle mass and function because the acute stress reaction.

Traditionally, muscle mass – a part of the concept of sarcopenia – is measured by computed tomography (CT) or dual-energy X-ray absorptiometry (DEXA) scan. These devices are not always easily available in clinical practice and cannot be used bedside. An innovation in sarcopenia is the assessment of muscle mass and quality with ultrasound. Because this device is much more available and applicable in all patients, diagnosis of acute sarcopenia would be much easier with ultrasound. Moreover, if other factors that contribute to accelerated decline in muscle mass and function can be determinated, we can screen for acute sarcopenia in those individuals and hopefully reverse this mechanism.

This is the first multicenter study that will investigate the role of acute illness on sarcopenia during hospitalisation, assessed through ultrasound.

## Abstract

Sarcopenia is a geriatric syndrome defined as progressive and generalized age-related muscle loss with decline in muscle mass and muscle function (either strength or performance). It is closely related to adverse outcomes such as frailty, reduced quality of life, increased risk of falling, more frequent hospitalisations and higher mortality. Acute sarcopenia is the decline of muscle mass and function following acute disease or hospitalisation, sufficiently to meet the criteria of sarcopenia.

Objectives: To assess the effect of hospitalisation and acute illness on muscle mass and function, and to assess which other factors contribute to the development of acute sarcopenia.

Study design and main outcome measures: This study is a prospective multicenter observational study. Patients admitted to acute geriatric wards of different European centers and hospitalised for at least 5 days will be included. Measurements of muscle mass will be performed via ultrasound. Measurements of muscle function will be done by hand grip strength using Jamar dynamometer and by gait speed using the 4-meter walking test, when feasible. Other parameters will be measured via file study, laboratory investigations or validated questionnaires. Activity levels during hospitalisation will be measured through pedometers.

Anticipated results: Decline of muscle mass and muscle characteristics secondary to hospitalisation. We also expect an association with reasons of hospitalisation, pre-existing conditions, laboratory results and nutritional status prior to hospitalisation on the decline in muscle parameters.

Conclusions: This study seeks to gain knowledge of the development of acute sarcopenia and its contributing factors.

## Keywords

Acute sarcopenia, assessment, ultrasound, older people, skeletal muscle

## Clinical trial registration number

????

## Abbreviations

CT, Computed Tomography; DEXA, Dual-energy X-ray absorptiometry; EWGSOP, European Working Group on Sarcopenia in Older People; BIA, bio-impedance analysis; MRI, magnetic resonance imaging; CIRS-G, Cumulative Illness Rating Scale for Geriatrics; CRP, C-reactive protein; 25-OH-vitamin D, 25-hydroxyvitamin D; MNA-SF, Mini-Nutritional Assessment – Short Form; GLIM, Global Leadership Initiative on Malnutrition; PASE, Physical Activity Scale of the Elderly; SDPAR, Seven Day Physical Activity Recall; NMES, Neuromuscular electrical stimulation; CRM, Calorie Restriction Mimetics; EM, Exercise Mimetics.

## 1. Introduction

Sarcopenia is a well-known concept in geriatric medicine, although the definition has changed somewhat in recent years. Currently, it is defined by the second meeting of the European Working Group on Sarcopenia in Older People (EWGSOP) as a muscle disease (muscle failure), with low muscle strength as principal determinant [1].

In a review report from the International Sarcopenia Initiative, the prevalence of sarcopenia was reported according to care setting. There was a prevalence of 1-29% in community-dwelling older people, 10% in older patients in acute hospital care and 14-33% in older residents in long-term care [2]. The variability of prevalence is mostly due to the difference in assessment methods and cut-off points used. Screening for sarcopenia is very relevant in all these settings because it is correlated with mortality, functional decline, a higher rate of falls and a higher incidence of hospitalization and institutionalization [3].

A hospitalization poses an extra risk factor for older adults in terms of physical decline. Bed rest has a negative effect on muscle mass and muscle function [4-6], more pronounced in older people than in young individuals [7]. Acute illness and/or acute stress can lead to reduced muscle mass and function because of hypercortisolism and increased cortisol/dihydroepiandrosteron ratio [8], oxidative stress and inflammation processes [9, 10]. Although some data exist on acute muscle changes [6, 7, 11, 12], this concept of an acute component of sarcopenia was only first mentioned in 2016 [13].

Acute sarcopenia, secondary to an acute stressful event followed by hospitalisation, might not always recover completely and may lead to development of chronic sarcopenia [6]. Patients who have already met the criteria of sarcopenia may also develop an acute-on-chronic sarcopenia syndrome [8]. Furthermore, sarcopenia is associated with an increased length of hospital stay [14, 15], which can create a negative health spiral.

In order to prevent sarcopenia, diagnosis is paramount. There are different methods to diagnose sarcopenia [16]. Cut-off points are available for bio-impedance analysis (BIA) and dual X-ray absorptiometry (DEXA) but both lack qualitative data on muscle. Computed tomography (CT) and magnetic resonance imaging (MRI) provide both qualitative and quantitative data [16, 17], but lack cut-off points and are usually not feasible in daily practice. Ultrasound can also offer an objective and standardized measure of muscle quantity and quality, and is suitable for use on an acute ward since it is easy to perform, cheap, reproducible and can be used bedside. Previous reviews concluded that ultrasound technique is valid for measuring muscle size compared with measurement instruments such as CT and MRI [18]. Although standardization for ultrasound muscle mass measurements in older adults have been a major problem, recent efforts have tried to nullify this problem [19].

### 1.1. Objective

The aim of this study is to investigate the effect of hospitalisation due to acute illness on muscle mass characteristics, assessed in older adults through ultrasound. The primary endpoint is the change of characteristics of muscle mass in function of time since admission. The secondary endpoint of the study is to identify health related parameters associated with the development of acute sarcopenia. Relevant determinants of the evolution of muscle

mass and muscle strength since admission (reason of hospitalisation, comorbidities and laboratory data) will therefore also be investigated.

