### 2.3.2. Muscle mass

In order to obtain reliable and consistent measurements, all ultrasonography will be done by an ultrasonographist that is trained to perform the measurements proposed. For the measurements, a linear probe of 5 cm width will be used. Frequency of the beam will be set on 12 MHz.

Patients should not have had any physical exercise in the 30 minutes before the measurement. Muscles should be completely relaxed and patients should be placed in the supine position, with hips in neutral position and knees fully extended. The dominant leg will be taken for the measurements. To calculate the relative muscle thickness values, the total length of muscle will be noted.

Ultrasonographic data of the four bellies of the quadriceps muscle (rectus femoris, vastus lateralis, vastus medialis, vastus intermedius) will be taken. Measuring points will be specified according to the propositions of the SARCUS-working group [19]. Muscle thickness, fascicle length, pennation angle, muscle cross-sectional area and echo-intensity of all muscles listed will be taken.

The first measurement will be taken as early as possible within 48 hours after admission at the latest. Follow-up measurements will be taken according to the type of ward the patient is admitted to. For patients that are expected to be hospitalized for a limited time (<5 days), the follow-up measurement will be done 3 days after initial measurement. For patients that are expected to be hospitalized for a longer time (>7 days), measurements will be repeated 7

days after initial measurement, to be repeated after another 7 days as long as the patient is hospitalized.

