## **2.4. Statistical analysis**

Databases will be kept up in a Microsoft Access database.

Statistical analysis will be done by using SPSS Statistics version 24. Descriptive analyses will be used for determining the clinical and demographic characteristics. A Kolmogorov-Smirnov test will be used to verify the normal distribution of the different variables. Further statistical analyses will be performed by Chi Square test, Fisher exact, Mann-Whitney U test or Fisher exact test, depending on the distribution and the nature of the variables analysed. P-values of  $\leq 0.05$  will be considered statistically significant.

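### The primary endpoint names no lead ultrasound measure, muscle or time point, which leaves at least 20 candidates per scan and lets the primary result be chosen after the data are seen

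*Combined protocol and SAP*

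**What the plan says.** Section 1.1 (Objective) defines the endpoint in one sentence: "The primary endpoint is the change of characteristics of muscle mass in function of time since admission". The characteristics are not listed there.

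Section 2.3.2 (Muscle mass) is the only place that lists what is measured:
- Muscles: "Ultrasonographic data of the four bellies of the quadriceps muscle (rectus femoris, vastus lateralis, vastus medialis, vastus intermedius) will be taken".
- Measures: "Muscle thickness, fascicle length, pennation angle, muscle cross-sectional area and echo-intensity of all muscles listed will be taken".
- Side: "The dominant leg will be taken for the measurements".
- A derived quantity is also planned: "To calculate the relative muscle thickness values, the total length of muscle will be noted".

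The same section sets the scan times. Patients with an expected stay under 5 days are rescanned 3 days after the first scan. Those with an expected stay over 7 days are rescanned at 7 days and then every further 7 days while in hospital. No scan is designated as primary.

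Section 2.4 (Statistical analysis) says that p-values at or below 0.05 "will be considered statistically significant". It names chi-square, Fisher exact and Mann-Whitney U tests. It gives no hierarchy, composite, global test or multiplicity adjustment.

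The expected result is directional. Section 1.2 (Hypothesis) predicts a negative effect on muscle mass and function, and the Abstract has "Anticipated results: Decline of muscle mass and muscle characteristics secondary to hospitalisation".

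**The concern.** A primary endpoint should fix, before the data are seen, which number answers the main question. Here any of the listed measures, in any belly, at any follow-up, could be put forward as that number. If rectus femoris thickness fell, vastus medialis cross-sectional area stayed flat and a pennation angle rose, the plan has no rule for saying what the primary finding is.

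The measures also describe different things. Thickness and cross-sectional area describe size, fascicle length and pennation angle describe architecture, and the Introduction separates muscle quantity from muscle quality. A significant change in a measure that is not a size measure could be presented as the primary finding on muscle mass.

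What is at stake is the credibility of the study's main claim, that hospitalisation for acute illness reduces muscle mass. A reader of the results could not tell a prespecified finding from the most favourable of many.

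**Working it through.** The plan states no sample size, power or overall error rate, so there is no figure of its own to reproduce.

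**Step 1: count the candidates.** Section 2.3.2 gives 5 measures, 4 muscles and 1 leg: 5 x 4 x 1 = 20 per scan. Relative muscle thickness would add to this, so 20 is a minimum.

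**Step 2: assumptions.** These are not in the documents: each of the 20 within-patient changes is tested two-sided at 0.05 at a single follow-up; none truly changes; the test statistics are jointly normal with a common pairwise correlation r.

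**Step 3: independent case.**
- Expected false positives: 20 x 0.05 = 1.
- At least one significant change in either direction: 1 - 0.95^20 = 1 - 0.3585 = 0.642.
- At least one significant decline (0.025 in that tail): 1 - 0.975^20 = 1 - 0.6027 = 0.397.

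**Step 4: correlated case.** Measures in one leg are correlated, so the independent figure is an upper illustration. Write each statistic as sqrt(r) x G + sqrt(1 - r) x E, with G shared by all 20 and E specific to each. The chance of no significant change in either direction, given G = g, is [Phi((1.96 - sqrt(r) g)/sqrt(1 - r)) - Phi((-1.96 - sqrt(r) g)/sqrt(1 - r))]^20. For no significant decline, only one tail is kept. Averaging over g by numerical integration, and subtracting from 1, gives:

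| Assumed r | Any change | Decline only |
|---|---|---|
| 0 | 64% | 40% |
| 0.3 | 54% | 28% |
| 0.5 | 42% | 21% |
| 0.7 | 29% | 14% |
| 0.8 | 22% | 11% |
| 0.9 | 16% | 8% |

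Intended rates for one prespecified test are 5% for any change and 2.5% for a decline. Every row exceeds them.

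**Step 5: what a remedy does.** One named measure, muscle and time definition returns the primary error rate to 5%. Keeping all 20 co-equal under Bonferroni means 0.05/20 = 0.0025 each. At 80% power the sample size ratio is ((3.023 + 0.842)/(1.960 + 0.842))^2 = (3.865/2.802)^2 = 1.9, so about 1.9 times as many patients.

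**The case against.** Several objections have force.

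- **The 20 values and the threshold are inferences.** A reader might infer that the protocol makes 20 measures the primary endpoint and applies 0.05 to each. It says neither. Section 1.1 does not tie its characteristics to the list in 2.3.2, and 2.4 gives one general threshold without mentioning the ultrasound measures. This stands as to wording. But no other list and no other decision rule exists, and the ambiguity is itself the gap.
- **The modelled tests are not in the plan.** Section 2.4 names tests for independent groups or categories, none for paired or repeated data. The percentages therefore illustrate an analysis that has to be supplied. This stands.
- **64% overstates the harm.** The hypothesis is directional, and 64% also counts false increases. This stands, and the decline-only column is the closer match to the claim.
- **Repeat scans need not multiply the tests.** Section 1.1 speaks of change over time, which one longitudinal model per measure could answer with a single test. So a multiplied count is not established. The choice of time point nevertheless remains open.
- **The direction of worsening.** A reader might say that the anticipated decline is the wrong direction for echo-intensity. The documents do not state which direction is worse for that measure, and the Abstract's wording can fairly be read as deterioration. That reading is not supported; what is missing is a stated direction for each measure.
- **Architecture and quality are in scope.** The aim speaks of muscle mass characteristics, and the Introduction values quantity and quality. Collecting these measures is deliberate and not at fault.
- **The study is observational.** Strict family-wise control is less binding here. But the protocol names a primary endpoint, states a hypothesis and sets a significance threshold, and choosing the lead measure afterwards harms an observational study too.

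**Conclusion.** The concern holds in this form: the primary endpoint is not tied to a measure, muscle or time point; at least 20 candidates per scan fit its wording; and no rule limits which may be reported as the primary result.

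If 20 changes with no true effect were each tested at one follow-up, the chance of at least one false decline would be 40% if independent and 28%, 21% and 11% at correlations of 0.3, 0.5 and 0.8, against an intended 2.5%. For a change in either direction the figures are 64%, 54%, 42% and 22%, against 5%. The tests, their two-sidedness and the correlations are assumptions; the documents give none of them. The case for change does not depend on the exact percentage. Even if muscle loss is real, which measure, by how much and when could still be selected afterwards.

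This should be corrected before analysis. It does not invalidate the data collection.

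**What to change.** Before analysis:

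1. In 1.1 and 2.3.2, name one size measure in one muscle as primary, for example rectus femoris thickness or cross-sectional area. The choice is the sponsor's.
2. Define the time element so that day 3 and day 7 scans are not pooled as if equal. A change from baseline to first follow-up would do exactly that. Two options are the change per day since admission from a mixed model using all scans, or the day 7 change in patients on the 7-day schedule. Section 2.3.2 gives no follow-up time for expected stays of 5 to 7 days, so say how those patients enter the analysis.
3. In 2.4, state the matching paired or repeated-measures analysis, since none of the tests now named addresses within-patient change.
4. Make the other measures, muscles and scans secondary and state the expected direction for each. Report them with confidence intervals, or with a Holm correction if they are tested.

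Cost: a few sentences in three sections and no change to the data collected. The headline claim then rests on one measure and the others become supportive. The day 7 option also confines the claim to patients on that schedule, and the per-day option assumes roughly linear change.

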## **1.2. Hypothesis**

Hospitalisation and acute illnesses will negatively affect both muscle mass and muscle function and will hereby contribute to the development of acute sarcopenia. We hypothesize that hospitalisation due to an elevated degree of inflammation will lead to more severe decrease of muscle mass and muscle function than hospitalisation due to non-inflammatory reasons. Furthermore, certain pre-existing conditions are supposed to increase the risk of acute sarcopenia.

## **2. Methods**

### **2.1. Study design**

A prospective, multicenter, international observational study will be conducted. The study is designed to determine the effect of hospitalisation due to acute illness on the changes in muscle mass and muscle function. The secondary endpoint of the study is to identify health related parameters associated with the development of acute sarcopenia.

### **2.2. Subjects**

#### **2.2.1. Inclusion criteria**

Patients admitted between the 1st of November 2018 until the 31th of October 2019 will be eligible for inclusion. Included wards for admission are: internal medicine, acute geriatrics, orthogeriatrics and rehabilitation. Age limit will be set on 65 years and older.

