## Appendix

**Table 1:** Inclusion and exclusion criteria for patient participation

Inclusion criteria	Exclusion criteria
Admitted from 01/11/2018 – 31/10/2019	Dialysis
65 years or older	Previous/actual stroke
	Actual hypo- or hyperthyroidism.
	Oedema of the lower limbs
	Severely dehydration
	Systemic connective tissue disorders 
 
• Polyarteritis nodosa and related conditions
 
• Other necrotizing vasculopathies
 
• Systemic lupus erythematosus
 
• Dermatopolymyositis
 
• Systemic sclerosis – scleroderma
 
• Other systemic involvement of connective tissue
 
• Systemic disorders of connective tissue in diseases classified elsewhere
 

	Myositis
	Calcification and ossification of muscle
	Systemic atrophies primarily affecting the central nervous system 
 
• Huntington's disease
 
• Hereditary ataxia
 
• Spinal muscular atrophy and related syndromes
 
• Systemic atrophies primarily affecting central nervous system in diseases classified elsewhere
 
• Postpolio syndrome
 

	Demyelinating diseases of the central nervous system 
 
• Multiple sclerosis
 
• Other acute disseminated demyelination
 
• Other demyelinating diseases of central nervous system
 

	The chronic use of oral corticosteroids

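### Eligibility does not require an acute illness, so the change since admission cannot be attributed to acute illness across the whole cohort, and acuity may be confounded with inflammation

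*Combined protocol and SAP*

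**What the plan says.** Section 1.1 gives the aim as to "investigate the effect of hospitalisation due to acute illness on muscle mass characteristics", and section 2.1 repeats it: "The study is designed to determine the effect of hospitalisation due to acute illness on the changes in muscle mass and muscle function". Section 4 (Conclusions) likewise speaks of acute illness followed by a hospital stay. The endpoint is defined within patients: "The primary endpoint is the change of characteristics of muscle mass in function of time since admission".

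Section 2.2.1 sets three conditions: an admission window, a ward and an age. The wards are listed as "Included wards for admission are: internal medicine, acute geriatrics, orthogeriatrics and rehabilitation", and the age rule is "Age limit will be set on 65 years and older". Table 1 in the Appendix keeps only the window ("Admitted from 01/11/2018 – 31/10/2019") and the age. The exclusions in section 2.2.2 and Table 1 concern diseases, oedema, dehydration and steroid use; none concerns the type of admission.

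Section 1.2 expects inflammatory admissions to show a "more severe decrease of muscle mass and muscle function than hospitalisation due to non-inflammatory reasons". Section 2.3.1 records the principal reason for admission, and CRP and white cell count are taken on the admission day. Section 1.1 lists the reason for admission among the determinants to be examined. Section 2.4 names chi-square, Fisher's exact and Mann-Whitney U tests, with no model, stratification or restricted analysis set.

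**The concern.** A person of 65 or over who comes in for elective joint surgery, a planned work-up or a planned rehabilitation stay meets every condition in section 2.2.1 and Table 1, unless one of the listed exclusions applies. Such a person lacks the exposure named in sections 1.1 and 2.1.

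Two results depend on this. First, the primary endpoint has no comparator group, so attributing the change to acute illness rests on who is enrolled. If some of the cohort was not acutely ill, the pooled change describes a mixture. Second, most planned admissions would be classed as non-inflammatory, whether that is judged by reason for admission or by admission-day CRP. The comparison would then partly set acutely ill patients against patients who were not acutely ill, and a larger sample would not remove that.

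**Working it through.** **The passages side by side**

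| Place | Exposure or population |
|---|---|
| Sections 1.1, 2.1, 4 | hospital stay caused by, or following, acute illness |
| Highlights, Abstract, section 3 | broader: hospitalisation or stressors also count |
| Section 1.2, first sentence | hospitalisation and acute illness named together |
| Abstract, population | acute geriatric wards, stay of at least 5 days |
| Section 2.2.1 | four ward types, no minimum stay |
| Table 1 | date and age only |

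The Abstract's population conflicts with section 2.2.1. It also conflicts with sections 2.3.2 and 2.3.3, which schedule follow-up for stays expected to last under 5 days. None of these places makes acute illness an entry condition.

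**Size: illustration only**

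The plan states no sample size, expected change or planned share, so there is no figure to reproduce. Every value below is an assumption.

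*Primary endpoint.* Let p be the planned share, and let A and P be the mean losses in acutely ill and planned patients.

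- Pooled loss = (1 − p)A + pP, so bias = p(P − A).
- If P = 0, the pooled loss is (1 − p)A: 90% of A at p = 10%, 70% at p = 30%, 50% at p = 50%.

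For precision, assume a standardised paired change of 0.3 in the acutely ill, P = 0, two-sided 0.05 and 80% power. With no planned patients, n = ((1.960 + 0.842)/0.3)² = 87.2, so 88. With planned share p, the standardised change becomes 0.3(1 − p)/√(1 + p(1 − p)·0.3²). At p = 30% this is 0.21/1.0094 = 0.208.

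| p | n for 80% power | Power at n = 88 |
|---|---|---|
| 0 | 88 | 80% |
| 10% | 109 | 71% |
| 20% | 139 | 61% |
| 30% | 182 | 50% |
| 50% | 357 | 29% |

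*Inflammation comparison.* Let I and N be the losses in inflammatory and non-inflammatory acute patients, and q the planned share of the non-inflammatory group.

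- Apparent difference = I − [(1 − q)N + qP], so bias relative to I − N is q(N − P).
- I = 6%, N = 4%, P = 1%, q = 0.5: group mean 0.5 × 4 + 0.5 × 1 = 2.5, apparent difference 6 − 2.5 = 3.5 points against 2.0.
- I = N = 4%, same P and q: 4 − 2.5 = 1.5 points, against zero.
- I = 6%, N = 4%, P = 0: 6 − 0.9 × 4 = 2.4 points at q = 10%, and 6 − 0.5 × 4 = 4.0 at q = 50%.
- I = N = 6%, P = 0: 6 − 0.9 × 6 = 0.6 points at q = 10%, and 6 − 0.5 × 6 = 3.0 at q = 50%.

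*Direction.* Both biases change sign with P. If planned patients lost more than the acute non-inflammatory ones, say P = 6% with N = 4% and q = 0.5, the bias would be 0.5 × (4 − 6) = −1.0, and a difference of 2.0 would appear as 1.0. If P is negative (patients gaining muscle), the pooled loss falls below the zero-loss case.

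**The case against.** The exposure is not consistently narrow. The Highlights, the Abstract, the first sentence of section 1.2 and section 3 treat hospitalisation or stressors as exposures in their own right, and elective surgery is arguably a stressor. Section 1.2 also does not confine its comparator to non-inflammatory acute illness, so planned admissions fit it as worded. The Abstract's population would shut out a planned rehabilitation stay or a short work-up. The data may allow these patients to be separated: reason for admission is recorded and listed as a determinant, and inflammatory markers are measured on admission.

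Most of this stands, and it limits the point. A reader might infer that planned admissions will dilute the primary effect and that the inflammation contrast will be falsely positive. The documents do not support either as fact. Sections 1 and 3 say bed rest itself reduces muscle, which weakens the zero-loss assumption. Rehabilitation patients may gain muscle, or may have lost it before the first scan. The 2.0-point reference in the illustration also belongs to a narrower comparison than section 1.2 literally states. Nor do the documents show that planned admissions must be barred: a strict entry rule could remove much of the rehabilitation ward, which section 2.2.1 names on purpose.

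What the objection does not remove is that sections 1.1 and 2.1 state an exposure that the entry rules do not secure, and that no analysis is pre-specified to separate those who had it. If the broader exposure was intended, those two sections are worded too narrowly, and planned patients still need to be identifiable.

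**Conclusion.** The point holds as a mismatch between the stated aim and the operative eligibility rules, together with inconsistent wording of the exposure and the population. Under the plan as written, change since admission cannot be attributed to acute illness for the whole cohort, and acuity may be confounded with inflammation because planned admissions would sit mainly in the non-inflammatory group.

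The extent is unknown. It depends on the planned share and on how much muscle planned patients lose relative to the acutely ill, and the plan gives neither. Upward bias in the inflammation contrast requires planned patients to lose less than acute non-inflammatory patients. That is plausible, but the documents do not establish it. This is a cheap improvement to the plan and does not by itself invalidate the design.

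**What to change.** 1. Reconcile the exposure wording in the Highlights, Abstract and sections 1.1, 1.2, 2.1, 3 and 4, and align the Abstract's population with section 2.2.1 and Table 1.
2. Add one field at entry in section 2.3.1: planned admission, or unplanned admission for acute illness or injury. Classify a transfer after an acute phase by its index admission, so that rehabilitation patients are not misclassified by the ward they reach.
3. State in section 2.4, before any data are examined, that the primary endpoint and the inflammation comparison are analysed in acute/unplanned admissions.
4. Report planned admissions as a separate group.

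The cost is one extra field and a smaller primary analysis population, by an amount the documents do not allow one to estimate. No ward has to be dropped. If the restriction were chosen only after the data were seen, it would be post hoc and carry less weight.
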